11.4.3 Multiplicity Adjustment for Primary and Key Secondary Endpoints

All analyses of the primary and two key secondary endpoints will focus on the comparison of tozadenant 120 mg BID vs. placebo followed by tozadenant 60 mg BID vs. placebo. The following six comparisons will be conducted using sequential testing with a fixed sequence, which controls the family-wise error for multiple comparisons at an alpha level of 0.05 (two-tailed):

- 1. Comparison of tozadenant 120 mg BID vs. placebo using the primary endpoint (Change from baseline to Week 24 in the number of hours per day spent in OFF state).
- 2. Comparison of tozadenant 120 mg BID vs. placebo using the first key secondary endpoint (Change from baseline to Week 24 in the number of hours per day spent in good ON time, defined as the sum of ON time without dyskinesia and ON time with non-troublesome dyskinesia).
- 3. Comparison of tozadenant 120 mg BID vs. placebo using the second key secondary endpoint (Change from baseline to Week 24 in UPDRS Parts II + III total score).
- 4. Comparison of tozadenant 60 mg BID vs. placebo using the primary endpoint (Change from baseline to Week 24 in the number of hours per day spent in OFF state).
- 5. Comparison of tozadenant 60 mg BID vs. placebo using the first key secondary endpoint (Change from baseline to Week 24 in the number of hours per day spent in good ON time, defined as the sum of ON time without dyskinesia and ON time with non-troublesome dyskinesia).
- 6. Comparison of tozadenant 60 mg BID vs. placebo using the second key secondary endpoint (Change from baseline to Week 24 in UPDRS Parts II + III total score).

Testing will begin with tozadenant 120 mg BID vs. placebo for change from baseline to Week 24 in the number of hours per day spent in OFF state. If the p-value is less than or equal to an $\alpha = 0.05$, then the result is considered statistically significant and testing will proceed to the next comparison, and so forth. Testing will stop with the first adjusted p-value >0.05 and that comparison, as well as any comparison later in the sequence will be considered not statistically significant.

The adjusted p-values p'_i for i = 1 to 6 will be calculated by taking the maximum of the raw p-value (p_i) from the statistical test and the adjusted p-value (p_{i-1}) from the prior test, as shown below:

P-values from the analyses of all other efficacy outcomes will be reported as nominal, with no adjustment for multiplicity.

11.4.4 Other Secondary Efficacy Analyses

The other secondary efficacy analyses include the change from Baseline to Week 24 (where applicable), for the following:

- 1. CGI-I.
- 2. PGI-I.
- 3. UPDRS Part III (motor subscale) score in the ON state.
- 4. Investigator global impressions of severity of illness (CGI-S).
- 5. UPDRS Part II (ADL subscale) score.
- 6. Number of hours per day spent in the ON state (without dyskinesia, with non-troublesome dyskinesia, or with troublesome dyskinesia).
- 7. Number of hours per day spent in the ON state without dyskinesia.
- 8. Number of hours per day spent in the ON state with any dyskinesia (troublesome or non-troublesome).
- 9. Number of hours per day spent in the ON state with non-troublesome dyskinesia.
- 10. PDQ-39 (total score and individual domain scores).
- 11. UPDRS Part IV.
- 12. UPDRS Part I.

All continuous other secondary efficacy variables will be analyzed using the model defined in the primary analysis of OFF time (Section 11.4.1) and the mITT. Sensitivity analyses of the other secondary efficacy variables are not planned.

All other variables will be analyzed using adequate statistical methods.

11.4.5 Exploratory Analyses (Part A)

The exploratory analyses in Part A include the change from Baseline to Week 24, for the following:

- 1. Number of hours per day spent in the asleep state.
- 2. Dyskinesia as measured by questions 32, 33 and 34 of UPDRS Part IV.
- 3. Falls as measured by question 13 on UPDRS Part II.
- 4. Responder analysis of number (%) of patients with ≥ 1.0 h improvement in OFF time (evaluated at Week 24).
- 5. Responder analysis of number (%) of patients with \geq 2.0 h improvement in OFF time (evaluated at Week 24).
- 6. Percent change in total levodopa equivalent dose.

- 7. Percent change in the number of hours per day spent in OFF state.
- 8. Percent change in the number of hours per day spent in ON state without troublesome dyskinesia.
- 9. Percent change in the number of hours per day spent in ON state with troublesome dyskinesia.
- 10. Scales for Outcomes in Parkinson's Disease–cognition (SCOPA-cog) score.
- 11. Fall questionnaire score.
- 12. Number of hours per day spent in the OFF state in the sub-population of subjects taking levodopa and only one additional concomitant anti-PD medication.
- 13. Number of hours per day spent in the OFF state in the sub-population of subjects taking levodopa and two additional concomitant anti-PD medications.
- 14. Number of hours per day spent in the OFF state in the sub-population of subjects taking levodopa and three additional concomitant anti-PD medications.
- 15. EQ-5D-5L.
- 16. TSQM-9 (evaluated at Weeks 6 and 24).

These analyses will be documented by descriptive statistics by treatment group in the mITT. No statistical analyses are planned.

11.4.6 Exploratory Analyses (Part B)

The exploratory analyses in Part B include the following:

- 1. Change from Baseline in UPDRS Part II (ADL subscale) + Part III (motor subscale) total score.
- 2. Change from Baseline in UPDRS Part II (ADL subscale) score.
- 3. Change from Baseline in UPDRS Part III (motor subscale) score in the ON state.
- 4. Change from Baseline in UPDRS Part I total score.
- 5. Change from Baseline in UPDRS Part IV total score.
- 6. Change from Baseline in dyskinesia as measured by questions 32, 33 and 34 of UPDRS Part IV.
- 7. Change from Baseline in SCOPA-cog score.
- 8. Change from Baseline in Fall questionnaire score.
- 9. Percent change from Baseline to the end of open-label treatment in total levodopa equivalent dose.

- 10. Exploratory Endpoints to Evaluate Potential Disease Modification:
 - 10.1 Compare the estimate of change from Baseline to Week 76 in UPDRS I-III score between patients who were randomized to tozadenant in Part A (early-start) and those who were randomized to placebo in Part A (late start) for each dose (60 mg and 120 mg BID).
 - 10.2 Test the noninferiority of the slope estimates from the UPDRS I-III score of the early-start and delayed-start tozadenant groups (60 mg and 120 mg BID) during Part B (Weeks 36–76).
 - 10.3 Compare the estimate of change from Baseline to Week 76 in the SCOPA-cog score between patients who were randomized to tozadenant in Part A (early-start) and those who were randomized to placebo in Part A (late start) for each dose (60 mg and 120 mg BID).
 - 10.4 Test the noninferiority of the slope estimates from the SCOPA-cog score of the early-start and delayed-start tozadenant groups (60 mg and 120 mg BID) during Part B (Weeks 36–76).
 - 10.5 Compare the estimate of change from Baseline to Week 76 in Fall questionnaire score between patients who were randomized to tozadenant in Part A (early-start) and those who were randomized to placebo in Part A (late start) for each dose (60 mg and 120 mg BID).
 - 10.6 Test the noninferiority of the slope estimates from the Fall questionnaire score of the early-start and delayed-start tozadenant groups (60 mg and 120 mg BID) during Part B (Weeks 36–76).
 - 10.7 Compare the estimate of change from Baseline to Week 76 in total daily levodopa equivalents between patients who were randomized to tozadenant in Part A (early start) and those who were randomized to placebo in Part A (late start) for each dose (60 mg and 120 mg BID).
 - 10.8 Test the noninferiority of the slope estimates from total daily levodopa equivalents of the early-start and delayed-start tozadenant groups (60 mg and 120 mg BID) during Part B (Weeks 36–76).
- 11. EQ-5D-5L.
- 12. TSQM-9 (evaluated at Week 76).

All continuous other secondary efficacy variables will be analyzed using the model defined in the primary analysis of OFF time (Section 11.4.1) and the mITT. Sensitivity analyses of the other secondary efficacy variables are not planned.

All other variables will be analyzed using adequate statistical methods.

11.5 Planned Safety and Other Analyses

11.5.1 Safety Analyses

The primary safety variables will be the occurrence of TEAEs including nonserious and serious TEAEs, and TEAEs leading to permanent withdrawal of study medication during the study.

All AEs will be presented by Medical Dictionary for Regulatory Activities (MedDRA) system organ class, high level term and preferred term. The data will be displayed as number of patients experiencing the AEs, percentage of patients and number of AEs.

Safety data, including AEs, vital signs, ECGs, ESS including assessment of episodes of sudden onset of sleep, C-SSRS, mMIDI, physical and neurological examination, clinical laboratory test results, and concomitant medications will be summarized descriptively for each treatment group and for the entire tozadenant group, where appropriate. The descriptive statistics will be provided for the observed data and for the change from Baseline at each measured time point. Tables will summarize AE data as appropriate by dose group. Note that counting will be by patient, not event and patients are only counted once within each MedDRA system organ class (SOC) or preferred term (PT).

Clinical laboratory tests results, vital signs, ECGs, dyskinesia as measured by questions 32, 33 and 34 of UPDRS Part IV, ESS, weight, physical and neurological examination results, and UPDRS will be summarized descriptively. Descriptive statistics will be presented for continuous variables utilizing the observed data and the change from baseline (at each measured time point). Frequencies and percentages will be presented for categorical variables. Laboratory test results will be classified as below the lower limit of normal, within normal limits and above the ULN. Shift tables will be used to summarize changes from Baseline to each visit by treatment group. Clinically significant physical or neurological examination findings and any clinically significant out-of-range laboratory tests are recorded as adverse events and will be documented in the AE summaries.

Analyses will be performed for the SS as randomized.

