3.1.3 Modified Intent-to-Treat Set (mITT)

The mITT will consist of all randomized patients who took at least 1 dose of study drug and had valid diaries at baseline and had valid diaries on at least 1 post-baseline visit. Patients will be accounted for in the treatment group to which they were originally randomized.

Summaries and/or analyses of all efficacy data will be done in the mITT.

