9.6.5 Exploratory Variables

The exploratory variables will be summarized by descriptive statistics by treatment group in the mITT. No statistical analyses are planned. The list of variables includes the change from Baseline to Week 24 (where applicable) for the following:

- 1. Number of hours per day spent in the asleep state.
- 2. Dyskinesia as measured by questions 32, 33 and 34 of UPDRS Part IV.
- 3. Falls as measured by question 13 on UPDRS Part II.
- 4. Responder analysis of number (%) of patients with ≥ 1.0 h improvement in OFF time (evaluated at Week 24).
- 5. Responder analysis of number (%) of patients with ≥ 2.0 h improvement in OFF time (evaluated at Week 24).
- 6. Percent change in total levodopa equivalent dose.
- 7. Percent change in the number of hours per day spent in OFF state.
- 8. Percent change in the number of hours per day spent in ON state without troublesome dyskinesia.
- 9. Percent change in the number of hours per day spent in ON state with troublesome dyskinesia.
- 10. Scales for Outcomes in Parkinson's Disease-cognition (SCOPA-cog) score.
- 11. Fall questionnaire score.
- 12. Number of hours per day spent in the OFF state in the sub-population of subjects taking levodopa and only one additional concomitant anti-PD medication.
- 13. Number of hours per day spent in the OFF state in the sub-population of subjects taking levodopa and two additional concomitant anti-PD medications.
- 14. Number of hours per day spent in the OFF state in the sub-population of subjects taking levodopa and three additional concomitant anti-PD medications.

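### The protocol calls for a Safety Set summary of UPDRS dyskinesia items 32–34 at every time point, but the SAP has only an exploratory Week 24 change in the mITT

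*Protocol*

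**What the plan says.** Protocol 11.5.1 (Safety Analyses) lists "dyskinesia as measured by questions 32, 33 and 34 of UPDRS Part IV, ESS, weight, physical and neurological examination results" with laboratory tests, vital signs, ECGs and UPDRS as data to be summarized descriptively. On content and timing it says "Descriptive statistics will be presented for continuous variables utilizing the observed data and the change from baseline (at each measured time point". On the analysis set it says "Analyses will be performed for the SS as randomized".

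Protocol 11.4.5 also lists items 32–34 as a Part A exploratory change to Week 24, and there "These analyses will be documented by descriptive statistics by treatment group in the mITT". The protocol therefore asks for two presentations of the same items: one as safety data and one as exploratory efficacy data.

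The SAP carries over only the second. In SAP 4.2.3 and 9.6.5 the items are exploratory: "The exploratory variables will be summarized by descriptive statistics by treatment group in the mITT", and "The list of variables includes the change from Baseline to Week 24 (where applicable) for the following". Entry to the mITT requires at least one dose, valid baseline diaries, and that the patient "had valid diaries on at least 1 post-baseline visit" (SAP 3.1.3). Neither the SAP's safety endpoints (4.3) nor its safety analyses (9.7.1 to 9.7.11) mention items 32–34.

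**The concern.** Tozadenant is added to levodopa, and the protocol's own diary definition describes dyskinesia as an effect of medication, so worsening dyskinesia is a tolerability question. Items 32–34 are the rater's systematic record of its duration, disability and pain. UPDRS is scheduled at Weeks 2, 6, 12, 18 and 24, and at Early Termination if dosing stopped no more than 24 hours earlier (protocol Table 1).

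If the SAP is followed as written, the only item-level table covers patients who reached Week 24 and met the diary rule. A patient whose items rose at Week 6 and who then left would not appear in it. The table also sits in a class of analyses that SAP section 8 leaves open to modification, whereas the protocol makes it part of the safety reporting.

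**Working it through.** **1. The two documents side by side, for items 32–34**

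| | Protocol 11.5.1 | SAP 9.6.5 |
|---|---|---|
| Role | Safety | Exploratory efficacy |
| Analysis set | Safety Set | mITT (diary-based) |
| Time points | Each one measured | Week 24 |
| Content | Observed values and change | Change from baseline |

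**2. Where the rest of the protocol sentence went.** Laboratory data, vital signs, weight, ESS, ECG and the physical and neurological examinations each have their own SAP section (9.7.3, 9.7.4, 9.7.5, 9.7.7, 9.7.10, 9.7.11). Blood pressure and pulse, weight, ECG and examinations explicitly include early termination. The UPDRS entries are the only ones in that sentence without a counterpart in SAP 9.7.

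**3. How many patients a Week 24 table can miss.** Protocol 3.1.2 gives 450 randomized and 80% completing.

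- Completers: 450 × 0.80 = 360, which reproduces the protocol's figure.
- Remainder: 450 − 360 = 90, or 20%.
- Per arm, if loss is equal across arms (an assumption): 90 / 3 = 30.

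The 80% covers patients who complete Part A and also continue into Part B. Someone who finishes Week 24 but declines Part B could still have a score at that visit, so 90 is approximate. Patients with no valid post-baseline diary cannot be counted from the documents. They may be few, because one valid diary day is enough for a visit (SAP 4.1).

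**4. Can the Part IV total stand in for the items?** From protocol Appendix 15.1, the maximum scores are:

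- Items 32, 33, 34: 3 × 4 = 12
- Items 35 to 38: 4 × 1 = 4
- Item 39 (share of the waking day OFF): 4
- Items 40 to 42: 3 × 1 = 3
- Total: 12 + 4 + 4 + 3 = 23

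Items 32–34 make up 12 of 23 points (52%). The drug is intended to reduce OFF time, so item 39 should fall if it works. A rise of 1 point in items 32–34 with a fall of 1 point in item 39 gives a net change of +1 − 1 = 0. The total can be flat while dyskinesia worsens.

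**5. Early Termination scores.** The mixed model in SAP 9.6.1 has weeks 2, 6, 12, 18 and 24 and no Early Termination level. Protocol 11.8 carries Early Termination data to the next visit, but states this for OFF time only. A diary is reviewed at Early Termination only when the visit coincides with a scheduled diary return, whereas UPDRS needs only the 24-hour condition. For a patient who leaves between scheduled visits, items 32–34 may be the only dyskinesia rating at exit. If that patient leaves before the first post-baseline diary, the patient is also outside the mITT.

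**The case against.** The strongest reply is that dyskinesia is well covered elsewhere. A reader might infer from the gap that dyskinesia in early leavers goes unreported; the documents do not support that.

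- SAP 9.7.1 tabulates treatment-emergent adverse events and those leading to discontinuation, and safety data use the Safety Set. The protocol names dyskinesia as an example of a pramipexole-related adverse event, so a patient who stops because of it should appear there.
- UPDRS Part IV score and diary ON time with any dyskinesia are analyzed with the primary mixed model over Weeks 2 to 24 (SAP 9.6.4). Early leavers in the mITT contribute their visits before leaving.
- The SAP's missing-item rule mentions Part IV sections A, B and C. Section A is items 32–35, so a dyskinesia subscore appears to be derived at each visit.

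The protocol is also not uniform. Its safety endpoint lists (2.2.6 and 11.2.2) omit items 32–34, as does another list within 11.5.1, and SAP 4.3 matches 2.2.6. The SAP was written to Amendment No. 1, while the supplied protocol is Amendment No. 3. It says it is to be read with the protocol, and table shells were to follow.

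Most of this stands, and it limits the consequence to item-level data. It does not close the gap. Adverse events come from open-ended prompts rather than a scale. The section A subscore is in no list of variables to be reported, and it includes item 35 as well. Both mixed models are confined to the mITT. Whatever Amendment No. 1 said, the current protocol text asks for a summary that the SAP does not contain.

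**Conclusion.** The point holds as a protocol–SAP mismatch in safety reporting. Following the SAP gives an item-level dyskinesia table restricted to mITT patients with a Week 24 value. Scores at Weeks 2 to 18 and at Early Termination, and those of patients outside the mITT for lack of a valid post-baseline diary, are in no planned table. About 90 of 450 patients (20%) would lack a Week 24 value, on the plan's completion rate and taking those who do not complete and continue to have no Week 24 score.

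Two stronger readings should be resisted. A reader might infer that the Week 24 table understates the arm difference by some percentage, or favors tozadenant. The documents give no dyskinesia dropout rate by arm, so any such figure would rest on invented inputs; the bias arises only if such dropout differs between arms. A reader might also infer that the SAP removed a protocol commitment. That cannot be shown, because the text of 11.5.1 under Amendment No. 1 is not available.

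No hypothesis test, alpha, power or sample size is affected. This should be corrected before database lock, but it does not threaten the primary result.

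**What to change.** Add a subsection to SAP 9.7 that implements protocol 11.5.1 for UPDRS Part IV items 32, 33 and 34, in the Safety Set, by arm and for all tozadenant:

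- observed value and change from baseline for each item at Weeks 2, 6, 12, 18 and 24, and at Early Termination where collected;
- a shift from baseline to worst post-baseline score, so that early leavers are counted. SAP 9.7.3 already does this for laboratory data. The protocol does not ask for it here; it is an addition.

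Keep the mITT Week 24 summary in 9.6.5 as exploratory. When the SAP is brought up to Amendment No. 3, add items 32–34 to the protocol and SAP safety endpoint lists so that all sections agree.

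The cost is one or two tables from data already collected. One limit remains: UPDRS is not done at Early Termination when dosing stopped more than 24 hours earlier, so those patients are represented only by their earlier visits, if any.

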11.5.2 Other Analyses

Patient Disposition

The number of patients who were screened, randomized, completed scheduled follow up, and prematurely withdrew study participation will be summarized overall and by treatment group. Reasons for non-participation and for withdrawal from study will also be presented.

Exposure to IMP/Compliance

The number of days of exposure to IMP will be summarized by treatment group. Compliance with IMP will be calculated as the number of doses taken divided by the scheduled number of doses taken, expressed as a percentage. Compliance will be summarized overall and by week for each treatment group.

Prior and Concomitant Medication Use

All prior and concomitant medications taken during the study period will be listed for each patient, including dosage and indication. Medications will be coded using the World Health Organization (WHO) Drug Dictionary Enhanced and classified as past medication (last dose taken prior to the first dose of IMP), concomitant medication ongoing at Baseline, or concomitant medication initiated after Baseline. The percentage of patients taking each medication (or class of medications) will be summarized overall and by treatment group.

Plasma Drug Concentrations

Results of the assays of tozadenant (and of pramipexole, in patients concomitantly taking pramipexole during the study) will be descriptively analyzed and reported in the clinical study report. Separate population analysis on the data from this study alone or combined with data from other studies as deemed appropriate will be performed and reported separately.

11.6 Unblinding Upon Completion of Part A

Immediately after Part A (double-blind phase) of the study completes and the database is cleaned and locked, the responsible CRO(s) will follow their SOPs to unblind Part A. A blinded data review will be performed (per ICH E9) before the database is locked and before the study groups are unblinded. Primary and secondary efficacy analyses are final and will not be modified. Exploratory analyses that do not involve the primary or secondary efficacy analyses are subject to modification.

11.7 Handling of Protocol Deviations

Important protocol deviations are deviations from the protocol which could potentially have a meaningful impact on either the primary efficacy or safety. The criteria for identifying important protocol deviations and the classification of important protocol deviations will be defined prior to unblinding. To the extent feasible, rules for identifying protocol deviations will be defined without review of the data and without consideration of the frequency of occurrence of such deviations. Whenever possible, criteria for identifying important protocol deviations will be implemented algorithmically to ensure consistency in the classification of important protocol deviations across all patients.

11.8 Handling of Dropouts or Missing Data

A valid diary will not have more than 2 hours (4 invalid entries) over a given 24-hour period. An invalid diary entry is defined as more than one entry recorded in a given half-hour interval, an unreadable entry, or the absence of an entry in a given half-hour interval. The average diary information from 3 valid diaries (if available) for each visit will be used to calculate diary-based efficacy endpoints. If there are only 2 valid diaries for a visit then the average information from the 2 valid diaries will be used. If only one diary is valid, information from the single valid diary

will be used. If no valid diaries are available for a patient visit then the diary information is considered missing.

For patients that prematurely withdrew from study, data collected during the Early Termination Visit will be used to impute 'OFF' time at the next visit. If the first diary day for a premature withdrawal visit was recorded more than one day after the last dose was administered, then the visit will not be used. The primary analysis of the primary efficacy variable will be based on an MMRM approach, hence visits beyond the Early Termination Visit will not to be imputed.

The total time 'OFF' will be determined by using the mean of the 3-day diary data immediately before each visit. A diary day will be regarded to be valid if at least 22 hours of the 24 hour clock are filled in. The missing hours will be imputed according to the proportions of being "on without dyskinesia", "on with troublesome dyskinesia", "on with non-troublesome dyskinesia", "off" and asleep. The visit data will be regarded to be valid if at least 2 days out of 3 are valid.

[figure not shown]
